#### A 1.1.3 Pharmacokinetic Concentration

Plasma concentrations and relevant parameters for ticagrelor and TAM will be summarized by control and group at each nominal time point for the PK Population using descriptive statistics such as mean, median, standard deviation, minimum, and maximum. Geometric mean (GM) and geometric coefficient of variation (GM CV %) will also be provided.

Individual ticagrelor and TAM plasma concentrations will be plotted on a linear and semi-log scale against actual sampling timepoints by. Mean ( $\pm$ SD) concentration of ticagrelor and TAM will be plotted on a linear and semi-logarithmic scale against nominal time points by group. The lower limit of quantification (LLOQ) will be plotted as a reference line on both individual and mean concentration plots.

Actual sampling times that are outside the sampling time windows may be excluded from concentration summary and mean concentration plotting but will still be used in the calculations of PK parameters and individual concentration plotting.

#### A 1.1.4 Pharmacokinetic Parameters

The following plasma PK parameters of ticagrelor and TAM will be determined with actual sampling time points using noncompartmental methods as appropriate:

Parameters	Description
AUC 0-t	Area under the plasma concentration vs time curve (AUC) from pre-dose (time 0) to the last quantifiable plasma concentration (C last )

No PK parameters will be calculated for subjects with 2 or fewer detectable concentrations in their PK profile.

AUC and plasma concentration for ticagrelor and TAM at each sampling timepoint (Pre-CPB, 30min, 60min, 90min, 120min, and post-CPB) will be compared between control and DrugSorb using a two-sample t-test, and if parametric assumptions are not met, then via a Mann-Whitney test.

The sample SAS code for this analysis is included here

```
proc ttest data=ADPP sides=2 alpha=0.05 h0=0;
  class TREATMENT;
  var log_PKParm;
  ods output ConfLimits=CL Statistics=Stat Ttests=Ttest;
```

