#### **5.3.1 Key Secondary Effectiveness Endpoints**

There is no imputation for the missing pre- or post-CPB blood ticagrelor levels, and analysis will be limited to subjects who have both samples.

Percent difference in pre-CPB vs. post-CPB blood ticagrelor levels as measured by LC/MS-MS is the key secondary effectiveness endpoint.

This endpoint will be evaluated using the two-sample t-test for the percentage change in blood ticagrelor levels between the treatment and the control group. The p-value and 95% CI for this treatment difference will be provided. The model assumption will be checked using the observed data.

If the post-CPB blood ticagrelor level is below the limit of quantification (BLQ), the BLQ value will be assigned.

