## 5.5 Exploratory Endpoints

All analyses will be performed on the mITT, PP, i-CABG mITT, and i-CABG PP populations.

The descriptive statistics will be summarized by treatment group for the exploratory endpoints.

Percent difference in pre-CPB vs. post-CPB blood TAM levels as measured by LC/MS-MS will be analyzed in the same fashion as blood ticagrelor levels (Section 5.3). Two-sample t-test for the percentage change in blood TAM between the treatment and the control group will be performed and the p-value and 95% CI for this treatment difference will be provided. Wilcoxon rank sum test based on the observed data will be performed as a sensitivity analysis. The nonparametric p-value will be provided as well as median treatment difference in percent change between pre-CPB and post-CPB blood TAM levels.

If the post-CPB blood TAM level is below the limit of quantification (BLQ), the BLQ value will be assigned. The Last Measurable Observation Carried Forward method will be implemented to test the validity of imputation.

ANOVA model will be employed to compare area under the concentration time curve (AUC) between the treatment groups, for intraoperative ticagrelor pharmacokinetic (PK) concentration and TAM based on the observed data.

The boxplots will be presented for the following exploratory endpoints by treatment.

- Operative time (measured from start of skin incision to completion chest closure)
- Duration of ICU stay
- Duration of hospital stay

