### A 1.1 Pharmacokinetic Assessment

#### A 1.1.1 Sample Collections for Pharmacokinetic Analysis

PK Blood samples will be collected for the determination of plasma ticagrelor and desethoxyhydroxy ticagrelor (ticagrelor active metabolite, TAM) concentration. The pre-CPB blood sample will be drawn prior to the start of CPB and can be up to 2hrs prior to skin incision. During the procedure, while the subject is on CPB, serial samples will be drawn at  $30\pm15$ min following initiation of CPB, at 60min, at 90min, and at 120min of CPB time. If the total CPB time required for the procedure is  $<120$ min (2hrs), the serial sampling will only be performed through the required duration of CPB. A post-CPB sample will be obtained as soon as possible following the end of CPB, and no later than 30min after the subject has been disconnected from the CPB circuit. The actual date and time of collection of each PK sample will be recorded.

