#### A 1.1.2 Handling Missing or Below the Lower Limit of Quantification Data

For PK concentration data, if the actual sampling time is missing, but a valid concentration value has been measured, the concentration value will be flagged, and the scheduled time point may be used for the calculation of PK parameters. In cases of missing concentration data, the missing data will not be imputed. For the individual concentration and PK parameter calculation of each group, the following rules will be applied:

- If BLQ values occur between measurable concentrations in a profile, the BLQ should be omitted (set to missing, and the time point is ignored in computations).
- If a BLQ value occurs after the last measurable concentration in a profile, the BLQ should be treated as missing data.
- If two BLQ values occur in succession after the last measurable value, the profile is deemed to have terminated at the first BLQ value and any subsequent concentrations and time points are omitted from pharmacokinetic calculations.

For the concentration summary and mean concentration plot preparation of each group, the following rules will be applied:

2. Mean concentration at any individual time point will only be calculated if at least half of the subjects have valid values (i.e., quantifiable and not missing) at this time point for each arm.

- In cases where a mean value is not calculated due to the above criterion not being met, the value will be set to missing.
- BLQ values will be set to zero.

GM and GM CV% will not be calculated if there are zero values for concentrations.

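### The exploratory AUC0-t is an inefficient comparison of the arms, mainly because it ignores the pre-CPB level, and its exclusion rule biases it toward no difference if unquantifiable values are common

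*SAP*

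**What the plan says.** The AUC of intraoperative ticagrelor concentration is an exploratory endpoint (Protocol 4.3.4, SAP 1.3.4). Protocol 11.3 specifies the trapezoidal approach.

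- **Window.** SAP A 1.1.4 integrates "from pre-dose (time 0) to the last quantifiable plasma concentration", using actual sampling times. SAP A 1.1.1 states: "The pre-CPB blood sample will be drawn prior to the start of CPB and can be up to 2hrs prior to skin incision". The listed points are "Pre-CPB, 30min, 60min, 90min, 120min, and post-CPB", so no sample is planned at CPB start. For CPB shorter than 120 min, "the serial sampling will only be performed through the required duration of CPB".
- **Values below the limit of quantification (BLQ).** For parameter calculation, SAP A 1.1.2 says: "If a BLQ value occurs after the last measurable concentration in a profile, the BLQ should be treated as missing data". For concentration summaries and mean plots they are set to zero. For the key secondary endpoint, SAP 5.3.1 says: "If the post-CPB blood ticagrelor level is below the limit of quantification (BLQ), the BLQ value will be assigned".
- **Exclusion.** SAP A 1.1.4: "No PK parameters will be calculated for subjects with 2 or fewer detectable concentrations in their PK profile".
- **Comparison.** SAP 5.5: "ANOVA model will be employed to compare area under the concentration time curve (AUC) between the treatment groups", with no scale stated. A 1.1.4 gives a two-sample t-test, or a Mann-Whitney test if assumptions fail, and its sample code uses a log-transformed parameter. Neither section divides AUC by elapsed time or adjusts for the pre-CPB level.

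For the key secondary endpoint, Protocol 11.3 chooses percent change because baseline levels in the bench studies were highly variable.

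**The concern.** Three features work against a clear reading of drug removal.

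1. The curve may include a stretch before CPB in which the arms cannot differ. That pulls the ratio toward 1.
2. Total AUC carries the full between-subject spread of starting concentration and of window length. The protocol recognises the first problem for percent change but does not carry the remedy over to AUC.
3. Having two or fewer detectable values is a post-randomisation result that effective removal makes more likely. Dropping those subjects can remove the strongest responders from the device arm.

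At stake is the only summary of the whole serial profile. A near-null AUC beside a clearly positive percent change could be read as conflicting evidence on mechanism when it is a property of the measure.

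**Working it through.** **The plan's nearest figure.** No power is stated for AUC. For the key secondary endpoint the SAP gives >99.9% (difference 40 points, SD 40; Protocol 11.1 uses 57 per arm). SE = 40·√(2/57) = 7.49; 40/7.49 = 5.34; power is 99.96% by noncentral t. This reproduces.

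**Dilution.** Inputs: 40% fall (Protocol 11.3), flat control arm (minimal change expected), exponential decline over an assumed 90 min of CPB, post-CPB sample taken at CPB end. Relative concentrations at 0.5, 1 and 1.5 h are 0.6^(1/3) = 0.843, 0.6^(2/3) = 0.711 and 0.600. With lead-in L hours:

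AUC(device) = (L + 0.5)(1 + 0.843)/2 + 0.25(0.843 + 0.711) + 0.25(0.711 + 0.600); AUC(control) = L + 1.5.

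| L (h) | Device | Control | Ratio | Log effect kept |
|---|---|---|---|---|
| 0 | 1.177 | 1.5 | 0.785 | 100% |
| 0.5 | 1.638 | 2.0 | 0.819 | 82% |
| 1 | 2.099 | 2.5 | 0.840 | 72% |
| 2 | 3.021 | 3.5 | 0.863 | 61% |
| 3 | 3.943 | 4.5 | 0.876 | 55% |

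On the raw scale the arithmetic difference grows, from 1.5 − 1.177 = 0.323 to 3.5 − 3.021 = 0.479 at L = 2. The trapezoid draws a straight line from the pre-CPB sample to the 30-min sample and so credits removal before CPB. Relative to control it still shrinks, from 21.5% to 13.7%.

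**Power.** Assumed, because the documents do not give them: baseline log-SD 0.5 or 1.0, lead-in, and CPB times. In simulations with 65 per arm, mean removal 40% (SD 40%) and lead-in 0.5-3 h, the geometric mean ratio was about 0.826 with the planned window and 0.742 from CPB start.

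Hand check for the planned window: ln 0.826 = −0.191 and SE = σ·√(2/65) = 0.175σ.

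- σ = 1.0: z = 1.09, power Φ(1.09 − 1.96) = 19%.
- σ = 0.5: z = 2.18, power Φ(0.22) = 59%.
- Adjusted for the pre-CPB level, residual σ = 0.30: z = 3.63, power 95%. At 0.35: z = 3.11, power 88%.

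Simulated power with no BLQ values (ranges cover different assumed lead-ins and CPB times):

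| Baseline log-SD | As planned | Start at CPB only | Baseline adjustment only | Full proposal |
|---|---|---|---|---|
| 0.5 | 43-63% | 78% | 96-99% | about 100% |
| 1.0 | 14-25% | 29-33% | 95% or more | about 100% |

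Moving time 0 alone recovers part of the loss. Adjustment recovers most of it. The adjusted figures need a residual log-SD of about 0.30 or less, and a wider spread of lead-ins would lower them.

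**Exclusion and BLQ rules.** Lead-in 0.5-3 h, mean removal 40%; the limit of quantification (LLOQ) is assumed as a share of median baseline. Ranges run from log-SD 0.5 to 1.0.

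| LLOQ | Excluded, device | Excluded, control | Ratio without the rules → with them |
|---|---|---|---|
| 1% | 0-0.2% | 0% | 0.820 → 0.820; 0.826 → 0.831 |
| 5% | 1.7-3.1% | 0-0.2% | 0.829 → 0.845; 0.830 → 0.875 |
| 20% | 10.7-17.7% | 0.1-5.9% | 0.826 → 0.900; 0.829 → 0.972 |

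In the last row, 65 × 0.107 = 7 device against about 0 control subjects are dropped at log-SD 0.5, and 65 × 0.177 = 11.5 against 65 × 0.059 = 3.8 at 1.0. Exclusion alone gives 0.906 and 0.981, and ending at the last quantifiable value brings these to 0.900 and 0.972. Truncation therefore acts slightly in the device's favour.

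**The case against.** The strongest reply is that little depends on this endpoint. AUC is exploratory and outside the sequence in SAP 3.7. Drug removal is tested by percent change, with a BLQ value assigned, a Wilcoxon sensitivity analysis and stated power >99.9%, and A 1.1.4 also compares concentrations at each timepoint. This stands.

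Two hours before incision is a maximum. The sample may be drawn at any time before CPB, and the protocol synopsis describes it as immediately before. This stands too: the lead-in could be short, and time 0 is undefined rather than fixed at 2 h.

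Several stronger readings are tempting, but the documents do not support them:

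- *The window biases the arms.* Lead-in and CPB time should be balanced by randomisation, so they dilute and add noise.
- *Stopping at the last quantifiable value hides removal.* It shortens device-arm curves and slightly favours the device.
- *The window explains the power gap.* Keeping the planned window but dividing by time and pre-CPB level gave 99-100% simulated power at log-SD 1.0. The missing baseline adjustment is the main cause.
- *Bias is certain.* It needs frequent BLQ values, and no LLOQ is given.
- *ANOVA and the t-test conflict.* With two groups and no covariates, ANOVA is the equal-variance t-test. Only the scale in SAP 5.5 is left open.
- *The BLQ rules contradict each other.* They are assigned to different outputs. A single rule for the comparison is preferable, but there is no contradiction to resolve.

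**Conclusion.** The point holds as a minor one: AUC0-t as planned is inefficient and possibly biased.

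- Dilution: with a 40% fall over 90 min, a 1-2 h lead-in leaves 61-72% of the log effect.
- Efficiency: the missing baseline adjustment causes most of the power loss. Power is about 20% against 95% or more at log-SD 1.0, and about 50-60% against 96-99% at 0.5.
- Bias: the exclusion rule pushes the ratio toward 1 when BLQ values are common, and has almost no effect at an LLOQ of 1% of median baseline.

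Baseline spread, lead-in, CPB times and LLOQ are all assumptions. A reader might infer that the trial cannot show drug removal. It can, through the key secondary endpoint and the timepoint comparisons, and no alpha-controlled conclusion changes.

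**What to change.** In SAP Appendix A:

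1. Define time 0 as CPB start and carry the pre-CPB value to it.
2. Analyse log time-averaged concentration (AUC divided by elapsed time) from CPB start to the post-CPB sample, adjusted for log pre-CPB level.
3. Impute BLQ values by one stated rule in both arms, for example LLOQ/2 with LLOQ as a sensitivity analysis, instead of setting them to missing.
4. Delete the exclusion for two or fewer detectable values, and report BLQ counts by arm.
5. State the log scale in SAP 5.5 so that it matches the Appendix code.

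The cost is minor rewording and programming. Actual sample times are already recorded, so no new data are needed. The remaining weakness is reliance on the pre-CPB value as the level at CPB start, which applies equally to both arms.

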## **A 2.0 Programming Specifications**

The creation of analysis datasets and all analyses will be performed using SAS® (version 9.4 or higher). PK parameters will be calculated via SAS® and confirmed with the results of Phoenix WinNonlin™ (version 8.1 or higher). All results within the tables, figures, and listings (TLFs), including the PK analyses, are validated through independent double programming.
